## 5.2.3 Trial Blinding/Masking

This is an open-label trial; therefore, the Sponsor, investigator and subject will know the treatment administered.

## 5.3 Randomization or Treatment Allocation

Patients who are enrolled on the phase II portion of the study and successfully complete the screening exams for initial registration will be randomized into one of two study arms. The study Biostatistician will generate a Flow Chart for Randomization. This Flow Chart will be held in confidence by the Biostatistician and the Clinical Trials Coordinator. The individual randomization assignment will be released by the Clinical Trials Coordinator only after the patient signs the informed consent document and successfully completes the screening process.

**Treatment of patients on Arm A**: Those patients randomized to Arm A will receive pembrolizumab alone.

**Treatment of patients on Arm B**: Those patients randomized to Arm B will receive pembrolizumab plus vorinostat.

#### 5.4 Stratification

The patients will be stratified by histology and PD-L1 status, including the following three levels of PD-L1 membranous expression on tumor cells that have been scientifically justified: 1) Proportion Score (PS)1-49%, and PS≥50%.

## 5.5 Concomitant Medications/Vaccinations (allowed & prohibited)

Medications or vaccinations specifically prohibited in the exclusion criteria are not allowed during the ongoing trial. If there is a clinical indication for one of these or other medications or vaccinations specifically prohibited during the trial, discontinuation from trial therapy or vaccination may be required. The investigator should discuss any questions regarding this with the Merck Clinical team. The final decision on any supportive therapy or vaccination rests with the investigator and/or the subject's primary physician.

## 5.5.1 Acceptable Concomitant Medications

All treatments that the investigator considers necessary for a subject's welfare may be administered at the discretion of the investigator in keeping with the community standards of medical care. All concomitant medication will be recorded in the source documentation including all prescription, over-the-counter (OTC), herbal supplements, and IV medications and fluids. If changes occur during the trial period, documentation of drug dosage, frequency, route, and date may also be included on the source documentation. Only those concomitant medications which are considered immunosuppressive such as steroids will be recorded in the CRF.

All concomitant medications received within 28 days before the first dose of trial treatment and 30 days after the last dose of trial treatment should be recorded. Concomitant medications administered after 30 days after the last dose of trial treatment should be recorded for SAEs as defined in Section 7.2 and ECIs as per the ECI guidance document.

#### **5.5.2** Prohibited Concomitant Medications

Subjects are prohibited from receiving the following therapies during the Screening and Treatment Phase (including retreatment for post-complete response relapse) of this trial:

- Antineoplastic systemic chemotherapy or biological therapy
- Immunotherapy not specified in this protocol
- Chemotherapy not specified in this protocol
- Investigational agents other than pembrolizumab
- Radiation therapy

- Note: Radiation therapy to a symptomatic solitary lesion or to the brain may be allowed at the investigator's discretion.
- Live vaccines within 30 days prior to the first dose of trial treatment and while participating in the trial. Examples of live vaccines include, but are not limited to, the following: measles, mumps, rubella, varicella/zoster, yellow fever, rabies, BCG, and typhoid vaccine.
- Systemic glucocorticoids for any purpose other than to modulate symptoms from an
  event of clinical interest of suspected immunologic etiology or to treat a comorbid
  condition as a standard of care (e.g. COPD exacerbation). The use of physiologic
  doses of corticosteroids may be approved after consultation with the Sponsor.
- HDAC inhibitors other than vorinostat.

Subjects who, in the assessment by the investigator, require the use of any of the aforementioned treatments for clinical management should be removed from the trial. Subjects may receive other medications that the investigator deems to be medically necessary.

The Exclusion Criteria describes other medications which are prohibited in this trial.

There are no prohibited therapies during the Post-Treatment Follow-up Phase.

## 5.6 Rescue Medications & Supportive Care

## 5.6.1 Supportive Care Guidelines

Subjects should receive appropriate supportive care measures as deemed necessary by the treating investigator. Suggested supportive care measures for the management of adverse events with potential immunologic etiology are outlined below and in greater detail in the ECI guidance document. Where appropriate, these guidelines include the use of oral or intravenous corticosteroids as well as additional anti-inflammatory agents if symptoms do not improve with administration of corticosteroids alone. Note that several courses of steroid tapering may be necessary as symptoms may worsen when the steroid dose is decreased. For each disorder, attempts should be made to rule out other causes such as metastatic disease or bacterial or viral infection, which might require additional supportive care. The treatment guidelines are intended to be applied when the investigator determines the events to be related to pembrolizumab.

Note: if after the evaluation the event is determined not to be related, the investigator is instructed to follow the ECI reporting guidance but does not need to follow the treatment guidance (as outlined in the ECI guidance document). Refer to Section 5.2.1 for dose modification.

It may be necessary to perform conditional procedures such as bronchoscopy, endoscopy, or skin photography as part of evaluation of the event. Suggested conditional procedures, as appropriate, can be found in the ECI guidance document.

#### Pneumonitis:

- For Grade 2 events, treat with systemic corticosteroids. When symptoms improve to Grade 1 or less, steroid taper should be started and continued over no less than 4 weeks.
- For Grade 3-4 events, immediately treat with intravenous steroids.
   Administer additional anti-inflammatory measures, as needed.
- Add prophylactic antibiotics for opportunistic infections in the case of prolonged steroid administration.
- $\circ$  A second episode of grade  $\geq$  2 pneumonitis mandates discontinuation of study therapy.

#### Diarrhea/Colitis:

Subjects should be carefully monitored for signs and symptoms of enterocolitis (such as diarrhea, abdominal pain, blood or mucus in stool, with or without fever) and of bowel perforation (such as peritoneal signs and ileus).

- All subjects who experience diarrhea/colitis should be advised to drink liberal quantities of clear fluids. If sufficient oral fluid intake is not feasible, fluid and electrolytes should be substituted via IV infusion. For Grade 2 or higher diarrhea, consider GI consultation and endoscopy to confirm or rule out colitis.
- For Grade 2 diarrhea/colitis that persists greater than 3 days, administer oral corticosteroids.
- o For **Grade 3 or 4 diarrhea/colitis** that persists > 1 week, treat with intravenous steroids followed by high dose oral steroids.
- When symptoms improve to Grade 1 or less, steroid taper should be started and continued over no less than 4 weeks.

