#### 5.2.1.2 Dose Modification

Adverse events (both non-serious and serious) associated with pembrolizumab exposure may represent an immunologic etiology. These adverse events may occur shortly after the first dose or several months after the last dose of treatment. Pembrolizumab must be withheld for drug-related toxicities and severe or life-threatening AEs as per **Table 7** below. See Section 5.6.1 and Events of Clinical Interest Guidance Document for supportive care guidelines, including use of corticosteroids.

Table 7. Dose Modification Guidelines for Drug-Related Adverse Events

Toxicity	Hold Treatment For Grade	Timing for Restarting Treatment	Discontinue Subject
Diarrhea/Colitis	2-3	Toxicity resolves to Grade 0-1.	Toxicity does not resolve within 12 weeks of last dose or inability to reduce corticosteroid to 10 mg or less of prednisone or equivalent per day within 12 weeks.
	4	Permanently discontinue	Permanently discontinue
AST, ALT, or Increased Bilirubin	2	Toxicity resolves to Grade 0-1	Toxicity does not resolve within 12 weeks of last dose.
	3-4	Permanently discontinue (see exception below) 	Permanently discontinue
Type 1 diabetes mellitus (if new onset) or Hyperglycemia	T1DM or 3-4	Hold pembrolizumab for new onset Type 1 diabetes mellitus or Grade 3- 4 hyperglycemia associated with evidence of beta cell failure.	Resume pembrolizumab when patients are clinically and metabolically stable.
Hypophysitis	2-3	Toxicity resolves to Grade 0-1	Toxicity does not resolve within 12 weeks of last dose or inability to reduce corticosteroid to 10 mg or less of prednisone or equivalent per day within 12 weeks.
	4	Permanently discontinue	Permanently discontinue
Hyperthyroidis m	3	Toxicity resolves to Grade 0-1	Toxicity does not resolve within 12 weeks of last dose or inability to reduce corticosteroid to 10 mg or less of prednisone or equivalent per day within 12 weeks.
	4	Permanently discontinue	Permanently discontinue
Hypothyroidism	2-4	Therapy with pembrolizumab can be continued while treatment for the thyroid disorder is instituted	Therapy with pembrolizumab can be continued while treatment for the thyroid disorder is instituted.
Infusion Reaction	3-4	Permanently discontinue	Permanently discontinue
Pneumonitis	2	Toxicity resolves to Grade 0-1	Toxicity does not resolve within 12 weeks of last dose or inability to reduce corticosteroid to 10 mg or less of prednisone or equivalent per day within 12 weeks.

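### Section 5.6.1 suggests steroids for Grade 3-4 diarrhea/colitis only after more than 1 week, 4 days later than its trigger for Grade 2

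*Combined protocol and SAP*

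**What the plan says.** The Diarrhea/Colitis part of Section 5.6.1 gives two steroid triggers. The first is "For Grade 2 diarrhea/colitis that persists greater than 3 days, administer oral corticosteroids". The second, for Grade 3 or 4, is "that persists > 1 week, treat with intravenous steroids followed by high dose oral steroids". The same part asks for monitoring for enterocolitis and perforation and for fluid replacement, and adds: "For Grade 2 or higher diarrhea, consider GI consultation and endoscopy to confirm or rule out colitis".

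The opening of Section 5.6.1 sets the status of this text. The measures are suggested, and they are "outlined below and in greater detail in the ECI guidance document". On scope it says: "The treatment guidelines are intended to be applied when the investigator determines the events to be related to pembrolizumab". For each disorder, "attempts should be made to rule out other causes such as metastatic disease or bacterial or viral infection".

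Section 5.2.1.2 deals with study drug: "Pembrolizumab must be withheld for drug-related toxicities and severe or life-threatening AEs". Its Table 7 holds treatment for Grade 2-3 diarrhea/colitis and stops it permanently at Grade 4. For steroids it refers elsewhere: "See Section 5.6.1 and Events of Clinical Interest Guidance Document for supportive care guidelines, including use of corticosteroids".

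**The concern.** The written trigger runs against severity: a milder event qualifies for steroids after 3 days, a severe or life-threatening one only after a week. A persistence condition is not in itself the fault, because Grade 2 has one as well. The fault is the order of the two.

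What is at stake is patient safety. A site that followed the bullets literally would start steroids later in the sicker patient. Table 10 in Section 7.2.4 describes Grade 3 as severe, with hospitalization indicated, and Grade 4 as life-threatening and needing urgent intervention. A wait of more than a week fits poorly with those definitions.

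**Working it through.** There is no planned figure to reproduce. The check sets the steroid rules of Section 5.6.1 side by side and takes one difference.

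| Event | Grade 2 | Grade 3-4 | Wait at Grade 3-4 |
|---|---|---|---|
| Pneumonitis | systemic steroids, no wait | IV steroids at once | none |
| Diarrhea/colitis | oral steroids after more than 3 days | IV, then high-dose oral, after more than 1 week | more than 7 days |
| Hypophysitis | steroids, no wait | IV, then oral | none |
| Hyperthyroidism | beta-blocker, no steroid named | IV, then oral | none |
| Hepatic | IV or oral steroids, no wait | IV for 1 to 2 days | none |
| Renal failure/nephritis | steroids, no wait | systemic steroids | none |

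1. Gap between the two diarrhea/colitis triggers: 7 - 3 = 4 days, with the later start at the higher grade.

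2. Is there an earlier Grade 3-4 trigger elsewhere? Not in the supplied text. The 3-day bullet names Grade 2 only. Read literally, a Grade 3 or 4 event on days 4 to 7 meets neither steroid trigger.

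3. Does Table 7 supply the timing? No. It governs when pembrolizumab is held or stopped, and the text above it sends the site to Section 5.6.1 and the ECI guidance document for corticosteroid use. In the protocol itself, the 5.6.1 bullet is therefore the stated timing.

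4. Does the need to exclude infection explain the longer wait? No. Section 5.6.1 asks for that step for every disorder, so it applies to Grade 2 diarrhea/colitis too and cannot account for a longer wait at Grade 3-4 alone.

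5. Effect of the change: a Grade 3-4 trigger of at most 3 days gives a gap of 3 - 3 = 0 days. With no wait, steroids could start up to 3 days before the Grade 2 trigger. Either removes the inversion.

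**The case against.** The strongest answer is that nothing here delays treatment of a sick patient. Section 5.6.1 only suggests measures. Section 5.5 leaves the final decision on supportive therapy to the investigator and/or the primary physician. Section 5.5.1 allows any treatment the investigator considers necessary, and Section 5.5.2 exempts steroids for suspected immune events from the prohibited list. Study drug is already held or stopped, perforation is watched for, and a GI work-up is considered. The ECI guidance document, which Section 7.2.3.2 describes as covering management of such events, may give an earlier start. Its absence from the file is not a fault of the plan.

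All of that stands as a limit on the consequence. It does not explain why the suggestion is ordered backwards. If the ECI document sets an earlier start, the two texts conflict. If it repeats the 5.6.1 timing, both need the same correction.

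A second answer is that the bullets name different treatments, so the 1-week bullet could be read as escalation for severe, persistent cases. The wording does not support that, because the 3-day bullet it would escalate from covers Grade 2 only.

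In the other direction, a reader might infer that the dose-limiting toxicity (DLT) rules in Section 8.2.2 already expect steroids within 3 days and so contradict Section 5.6.1. They do not. The 3-day clause for Grade 3 immune-related events excludes colitis, since Grade 3 or higher colitis is a DLT outright. The clause also classifies toxicities; it sets no deadline for starting steroids.

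**Conclusion.** The point holds for the wording: the Grade 3-4 steroid trigger for diarrhea/colitis is 4 days later than the Grade 2 trigger and is the only Grade 3-4 steroid rule among the six compared that carries a wait. Confidence in this is high. Confidence that steroids would start late in practice is moderate, because it depends on investigator judgment and on an ECI document that cannot be checked here.

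Few patients are likely to be affected, but the documents do not allow a count. A reader might take the 6% of 217 patients with drug-related Grade 3/4 events, reported in Section 4.2.1, as a ceiling. That figure covers events of every kind on pembrolizumab alone at 10 mg/kg, and it does not estimate Grade 3-4 diarrhea/colitis on the combination. In the 38-patient study in the same section, the only Grade 3/4 event was pulmonary edema. Neither study gives a rate for events lasting more than a week.

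No endpoint, sample size or analysis is touched. A reader might also infer that the protocol forbids earlier steroids, and it does not. This is a correction the sponsor should make, to one bullet of suggested safety guidance.

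**What to change.** Reword the Grade 3 or 4 bullet in the Diarrhea/Colitis part of Section 5.6.1 so that intravenous steroids followed by high-dose oral steroids start no later than the Grade 2 trigger, that is, after at most 3 days. Starting without a wait, as for the other Grade 3-4 events in the table, is also acceptable. It goes beyond what is needed to restore the order, so the choice is a clinical one. Keep the step of considering infection and other causes first.

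Then compare the new wording with the ECI guidance document so that a site finds one timing in both places. Section 8.2.2 needs no change.

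The cost is an edit to one bullet and that comparison, with whatever approval Section 10.13 requires. No patients or procedures are added. The downside is possibly earlier steroid use in some Grade 3-4 cases, which Section 5.6.1 already accepts for the other severe events it treats with steroids.

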# • Type 1 diabetes mellitus (if new onset, including diabetic ketoacidosis [DKA]) or ≥ Grade 3 Hyperglycemia, if associated with ketosis (ketonuria) or metabolic acidosis (DKA)

- For T1DM or Grade 3-4 Hyperglycemia
  - Insulin replacement therapy is recommended for Type I diabetes mellitus and for Grade 3-4 hyperglycemia associated with metabolic acidosis or ketonuria.
  - Evaluate patients with serum glucose and a metabolic panel, urine ketones, glycosylated hemoglobin, and C-peptide.

## • Hypophysitis:

- For Grade 2 events, treat with corticosteroids. When symptoms improve to Grade 1 or less, steroid taper should be started and continued over no less than 4 weeks. Replacement of appropriate hormones may be required as the steroid dose is tapered.
- For Grade 3-4 events, treat with an initial dose of IV corticosteroids followed by oral corticosteroids. When symptoms improve to Grade 1 or less, steroid

taper should be started and continued over no less than 4 weeks. Replacement of appropriate hormones may be required as the steroid dose is tapered.

#### Hyperthyroidism or Hypothyroidism:

Thyroid disorders can occur at any time during treatment. Monitor patients for changes in thyroid function (at the start of treatment, periodically during treatment, and as indicated based on clinical evaluation) and for clinical signs and symptoms of thyroid disorders.

- o **Grade 2** hyperthyroidism events (and **Grade 2-4** hypothyroidism):
  - In hyperthyroidism, non-selective beta-blockers (e.g. propranolol) are suggested as initial therapy.
  - In hypothyroidism, thyroid hormone replacement therapy, with levothyroxine or liothyroinine, is indicated per standard of care.
- o **Grade 3-4** hyperthyroidism
  - Treat with an initial dose of IV corticosteroid followed by oral corticosteroids. When symptoms improve to Grade 1 or less, steroid taper should be started and continued over no less than 4 weeks. Replacement of appropriate hormones may be required as the steroid dose is tapered.

#### Hepatic:

- For Grade 2 events, monitor liver function tests more frequently until returned to baseline values (consider weekly).
  - Treat with IV or oral corticosteroids
- For Grade 3-4 events, treat with intravenous corticosteroids for 24 to 48 hours.
- When symptoms improve to Grade 1 or less, a steroid taper should be started and continued over no less than 4 weeks.

#### Renal Failure or Nephritis:

- o For **Grade 2** events, treat with corticosteroids.
- o For **Grade 3-4** events, treat with systemic corticosteroids.
- When symptoms improve to Grade 1 or less, steroid taper should be started and continued over no less than 4 weeks.
- Management of Infusion Reactions: Signs and symptoms usually develop during or shortly after drug infusion and generally resolve completely within 24 hours of completion of infusion.

**Table 8** below shows treatment guidelines for subjects who experience an infusion reaction associated with administration of pembrolizumab (MK-3475).

**Table 8. Infusion Reaction Treatment Guidelines** 

NCI CTCAE Grade	Treatment	Premedication at subsequent dosing
Grade 1	Increase monitoring of vital signs as	None
Mild reaction; infusion interruption	medically indicated until the subject is	None
not indicated; intervention not	deemed medically stable in the opinion of the	
indicated	investigator.	
Grade 2	Stop Infusion and monitor symptoms.	Subject may be premedicated
Requires infusion interruption but	Additional appropriate medical therapy may	1.5h (± 30 minutes) prior to
	include but is not limited to:	infusion of pembrolizumab (MK-
responds promptly to symptomatic treatment (e.g., antihistamines,	IV fluids	3475) with:
NSAIDS, narcotics, IV fluids);	Antihistamines	3473) Witti.
	NSAIDS	Dinhanhydramina 50 mg na (ar
prophylactic medications indicated for < =24 hrs		Diphenhydramine 50 mg po (or
for < =24 nrs	Acetaminophen Narcotics	equivalent dose of
		antihistamine).
	Increase monitoring of vital signs as	A t
	medically indicated until the subject is	Acetaminophen 500-1000 mg
	deemed medically stable in the opinion of the	po (or equivalent dose of
	investigator.	antipyretic).
	If symptoms resolve within one hour of	
	stopping drug infusion, the infusion may be	
	restarted at 50% of the original infusion rate	
	(e.g., from 100 mL/hr to 50 mL/hr).	
	Otherwise dosing will be held until symptoms	
	resolve and the subject should be	
	premedicated for the next scheduled dose.	
	Subjects who develop Grade 2 toxicity	
	despite adequate premedication should	
	be permanently discontinued from further trial treatment administration.	
Crades 2 as 4		No subsequent desires
Grades 3 or 4	Stop Infusion.	No subsequent dosing
	Additional appropriate medical therapy may include but is not limited to:	
Grade 3:	IV fluids	
Prolonged (i.e., not rapidly	Antihistamines	
responsive to symptomatic	NSAIDS	
medication and/or brief interruption		
of infusion); recurrence of	Acetaminophen Narcotics	
symptoms following initial	Oxygen	
improvement; hospitalization	Pressors	
indicated for other clinical sequelae	Corticosteroids	
(e.g., renal impairment, pulmonary		
infiltrates)	Epinephrine	
	Increase monitoring of vital signs as	
Grade 4:	medically indicated until the subject is	
Life-threatening; pressor or	deemed medically stable in the opinion of the	
ventilatory support indicated	investigator.	
	Hospitalization may be indicated.	
	Subject is permanently discontinued from	
	further trial treatment administration.	
Appropriate resuscitation equipment	should be available in the room and a physician	readily available during the period
of drug administration.	Should be available in the room and a physician	readily available during the period
5. 4.45 Adminionation.		

## 5.7 Diet/Activity/Other Considerations

#### 5.7.1 *Diet*

Subjects should maintain a normal diet unless modifications are required to manage an AE such as diarrhea, nausea or vomiting.

## 5.7.2 Contraception

Pembrolizumab may have adverse effects on a fetus in utero. Furthermore, it is not known if pembrolizumab has transient adverse effects on the composition of sperm. Non-pregnant, non-breast-feeding women may be enrolled if they are willing to use 2 methods of birth control or are considered highly unlikely to conceive. Highly unlikely to conceive is defined as 1) surgically sterilized, or 2) postmenopausal (a woman who is ≥45 years of age and has not had menses for greater than 1 year will be considered postmenopausal), or 3) not heterosexually active for the duration of the study. The two birth control methods can be either two barrier methods or a barrier method plus a hormonal method to prevent pregnancy. Subjects should start using birth control from study Visit 1 throughout the study period up to 120 days after the last dose of study therapy. Male subjects should agree to use an adequate method of barrier contraception starting with the first dose of study therapy through 120 days after the last dose of study therapy.

The following are considered adequate barrier methods of contraception: diaphragm, condom (by the partner), copper intrauterine device, sponge, or spermicide. Appropriate hormonal contraceptives will include any registered and marketed contraceptive agent that contains an estrogen and/or a progestational agent (including oral, subcutaneous, intrauterine, or intramuscular agents).

Subjects should be informed that taking the study medication may involve unknown risks to the fetus (unborn baby) if pregnancy were to occur during the study. In order to participate in the study they must adhere to the contraception requirement (described above) for the duration of the study and during the follow-up period defined in section 7.2.2-Reporting of Pregnancy and Lactation to the Sponsor and to Merck. If there is any question that a subject will not reliably comply with the requirements for contraception, that subject should not be entered into the study.

